	Management of gestational diabetes - Reason for non availability in [aa002calc]	5	Staff shortage		
		6	Staff do not have the skills to offer the procedure		
		99	Other reason		
42052	Provide advice and support regarding	1	Yes		
da053	breastfeeding - Available in [aa002calc]	0	No		
		5	Staff shortage		
da054	Provide advice and support regarding breastfeeding - Reason for non availability in [aa002calc]	6	Staff do not have the skills to offer the procedure		
		99	Other reason		
1 055	Offer post-partum contraception -	1	Yes		
da055	Available in [aa002calc]	0	No		
		0	All clients refusal/not willing (if available but not performed)		
4.050	Offer post-partum contraception -	3	No contraceptives available		
da056	Reason for non availability in [aa002calc]	5	Staff shortage		
	[dautozcaic]	6	Staff do not have the skills to offer the procedure		
		99	Other reason		
1.057	Monitor newborn growth - Available in	1	Yes		
da057	[aa002calc]	0	No		
	Monitor newborn growth - Reason for non availability in [aa002calc]	2a	No weighing scale (baby)		
		2b	No height measure		
		2c	No tape measure		
da058		5	Staff shortage		
		6	Staff do not have the skills to offer the procedure		
		99	Other reason		
42050	Clinical examination of the mother and	1	Yes		
da059	baby - Available in [aa002calc]	0	No		
	Clinical examination of the mother and baby - Reason for non availability in [aa002calc]	2	No examination area		
da060		5	Staff shortage		
		6	Staff do not have the skills to offer the procedure		
		99	Other reason		
da061	Provide advice on danger signs postnatally in the mother and baby - Available in [aa002calc]	1	Yes		
		0	No		
	Provide advice on danger signs postnatally in the mother and baby - Reason for non availability in [aa002calc]	5	Staff shortage		
da062		6	Staff do not have the skills to offer the procedure		
		99	Other reason		

VARIABLE	QUESTION	VALUE	ANSWER
ea001	Number of women using ANC services who had their blood pressure measured in [aa002calc]		
ea002	Number of women using ANC services with high blood pressure in [aa002calc]		
ea003	Number of women using ANC services who had their urine tested for protein in [aa002calc]		
ea004	Number of women using ANC services who tested positive for proteinuria in [aa002calc]		
ea005	Number of women using ANC services who had their haemoglobin measured in [aa002calc]		
ea006	Number of women using ANC services who had low haemoglobin (<10g/dL) in [aa002calc]		
ea007	Number of women using ANC services with low Hb who received treatment in [aa002calc]		
ea008	Number of women using ANC services who were tested for malaria in [aa002calc]		
ea009	Number of women using ANC services who tested positive for malaria in [aa002calc]		
ea010	Number of women using ANC services who tested positive and received treatment for malaria in [aa002calc]		
ea011	Number of women using ANC services that received SP for malaria prophylaxis (IPT) in [aa002calc]		
ea012	Number of women using ANC services tested for HIV (rapid and/or lab testing) in [aa002calc]		
ea013	Number of women using ANC services who tested positive for HIV (rapid and/or lab testing) in [aa002calc]		
ea014	Number of women using ANC services who tested positive and received HIV treatment in [aa002calc]		

VARIABLE	QUESTION	VALUE	ANSWER
ea015	Number of HIV positive women using ANC services who received prophylactic ART for Prevention of Mother-To-Child Transmission (PMTCT) in [aa002calc]		
ea016	Number of women using ANC services tested for syphilis in [aa002calc]		
ea017	Number of women using ANC services who tested positive for syphilis in [aa002calc]		
ea018	Number of women using ANC services who tested positive and received syphilis treatment in [aa002calc]		
fa001	Number of women using PNC services who had their haemoglobin measured in [aa002calc]		
fa002	Number of women using PNC services who had low haemoglobin (<11g/dL) in [aa002calc]		
fa003	Number of women using PNC services with low Hb who received treatment in [aa002calc]		
fa004	Number of women using PNC services who were tested for malaria in [aa002calc]		
fa005	Number of women using PNC services who tested positive for malaria in [aa002calc]		
fa006	Number of women using PNC services who tested positive and received malaria treatment in [aa002calc]		
fa007	Number of women using PNC services tested for HIV (rapid and/or lab testing) in [aa002calc]		
fa008	Number of women using PNC services who tested positive for HIV (rapid and/or lab testing) in [aa002calc]		
fa009	Number of women using PNC services who tested positive and received HIV treatment in [aa002calc]		
fa010	Number of HIV positive women using PNC services who received prophylactic ART for Prevention of Mother-To-Child Transmission (PMTCT) in [aa002calc]		

VARIABLE	QUESTION	VALUE	ANSWER
fa011	Number of women using PNC services tested for syphilis in [aa002calc]		
fa012	Number of women using PNC services who tested positive for syphilis in [aa002calc]		
fa013	Number of women using PNC services who tested positive and received syphilis treatment in [aa002calc]		

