3.4 Outcomes

This trial will have two primary outcomes, one around essential components for ANC, and one for essential components for PNC.

Outcome 1 (ANC): Essential components included in the composite measure of integrated services specific to ANC visits are listed below.

- EC1 = Respectful maternity care indicators:
 - Introductions, greeting the woman, consent, questions
- EC2 = Screening for Pre-eclampsia:
 - Measure BP

- Test urine for proteinuria
- EC3 = Screening for, prevention and management of Anaemia:
 - Measure Haemoglobin
 - Provide ferrous sulphate with folic acid
- EC4 = Screening for, prevention and management of Malaria:
 - Checked for clinical symptoms and test for Malaria if relevant
 - Provide treatment if needed
 - Provide bed nets if not provided yet
 - Provide Intermittent Presumptive treatment
- EC5 = Screening for, prevention and management of HIV:
 - Test for HIV
 - Provide Prevention of mother to child transmission care (PMTCT)
 - Provide anti-retroviral drugs (ARV) for mother if needed
- EC6 = Screening for, prevention and management of Syphilis:
 - Test for syphilis
 - Provide antibiotics if needed
- EC7 = Screening for, prevention and management of Tuberculosis (TB):
 - Checked for clinical symptoms and test for TB
 - First line TB drugs or referral if needed
- EC8 = Prevention of Tetanus in mother:
 - Tetanus toxoid vaccination
- EC9 = Screening and counselling for mental health and domestic violence:
 - Screening tools
 - Counselling services
- EC10 = Estimation of BMI:
 - Assess maternal height
 - Assess maternal weight
- EC11 = Prevention of post- and pre-term birth:
 - Estimate gestational age
- EC12 = Assessment of foetal wellbeing during pregnancy, Screening for multiple pregnancy, abnormal lie and presentation during pregnancy:
 - Assess growth using fundal height measurement
 - Assess foetal heart rate (FHR)
 - Abdominal palpation
- EC13 = Provide advice on birth preparedness and danger signs of pregnancy:
 - Consultation

The outcome for each ANC visit will be a score which measures the proportion of the above components that was delivered during that visit (EC_ANC).

The score will measure the proportion of essential components delivered in full. All thirteen essential components listed above are applicable for ANC. Some essential components

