involve multiple components, at least one of which is always applicable; some components are only applicable to a subset of clients, eg HCP counsels the woman about mental health is only applicable if the client's response to a previous question is cause for concern. All essential components will carry a weight of 1. The overall score will be derived by aggregating the weighted scores for each essential component which will then be converted to a percentage. Six essential components are binary; hence the score can only be 0 (not achieved), or 1 (achieved and single weighted); in some cases the determination of this involves an algorithm. The other seven essential components are not binary as they have sub-components assessed independently and thus may be partially achieved and carry an intermediate score, eg a multiple of 0.25 for essential component 1 (respectful maternal care).

Outcome 2: Essential components included in the composite measure of integrated services specific to PNC visits are listed below.

- EC1b = Respectful maternity care indicators:
 - Introductions, greeting the woman, consent, questions
- EC2b = Screening for Pre-eclampsia:
 - Measure BP
- EC3b = Screening for, prevention and management of Anaemia:
 - Measure Haemoglobin
 - Provide ferrous sulphate with folic acid
- EC4b = Screening for, prevention and management of Malaria:
 - Checked for clinical symptoms and test for Malaria if relevant
 - Provide bed nets if not provided yet
- EC5b = Screening for, prevention and management of HIV:
 - Test for HIV
 - Provide Prevention of mother to child transmission care (PMTCT)
 - Provide anti-retroviral drugs (ARV) for mother and baby
- EC6b = Screening for, prevention and management of Syphilis:
 - Test for syphilis
 - Provide antibiotics if needed
- EC7b = Screening for, prevention and management of Tuberculosis (TB):
 - Checked for clinical symptoms and test for TB
 - First line TB drugs or referral if needed
- EC8b = Prevention of Tetanus in mother and baby:
 - Tetanus toxoid vaccination
- EC9b = Screening and counselling for mental health and domestic violence:
 - Screening tools
 - Counselling services
- EC10b = Provide advice and support regarding breastfeeding:
 - Consultation

- EC11b = Offer postpartum contraception:
 - Consultation
- EC12b = Monitor newborn growth:
 - Weigh the baby
- EC13b = Clinical examination of the mother:
 - Examine the mother
- EC14b = Clinical examination of the baby:
 - Examine the baby

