Appendix 2: Tools for data collection for observation

Below is the observation checklist. Essential components are numbered slightly differently than appendix 1 for the construction of the score. The scoring attributes will not appear for the data collectors and only be used by the statistician at time of analysis. Each essential component is score 1, for a total of 13 essential components for ANC visits, and 16 for PNC visits. Essential components can be a sum of x number of subcomponents as indicated in the table. Each subcomponent needs all applicable questions to be observed (Please see examples of algorithms at the end of appendix).

Please note this tool is to be deployed on an electronic platform, therefore the formatting of the tool will be visually different to what is included here. All boxes starting with "If" will only appear depending on the answer to the relevant condition (e.g. treatment will only be asked for women tested positive). The "Not applicable" answer is available for questions which depend on the gestational age and type of visit. The tool will be deployed in FRENCH.

OBSERVATION

Variable label	Answers	Conditionality	Scoring
GENERAL			
Please select the region	[dropdown menu]		
Please select the name of the facility	[dropdown menu]		
If 'Other' facility, please specify	[free text]		
Date of survey	[select from calendar]		
Name of person completing form	[free text]		
Anonymous ID of HCP	[free text]		
ANC			
ANC general information			
First/subsequent contact	0 - Subsequent contact, 1 - first contact -99 INF		
Which subsequent visit was it?	2- ANC2, 3- ANC3, 4- ANC4, 5- ANC5, 6-ANC6, 7- ANC7, 7-ANC8	Only to appear if previous answer = 0 – Subsequent visit	
Gestational age (weeks)	[integer]		
Who gave information about gestational age	1 - Woman, 2 - Healthcare provider, 3 - Other (specify)		
If other, specify	[free text]		
Women arrival time in the facility	[time]		
Comments	[free text]		

ANC contact		
EC1: Respectful maternity		1 (sum of all
care		subcomponents)
RMC subcomponent 1		0.25 (Points given if all applicable questions are observed)
The healthcare provider		
(HCP) introduced		
themselves to the		
pregnant woman	0 - No, 1 - Yes	
The HCP greeted the		
pregnant woman (or		
answered if woman		
greeted first)	0 - No, 1 – Yes	
RMC subcomponent 2		 0.25
The HCP asked the		
pregnant woman to take a	0 - No, 1 - Yes, -88 - Not	
seat	applicable (no chairs)	
The HCP asked the		
pregnant woman if she		
came with a companion		

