(or the woman already		
declared it herself)	0 - No, 1 – Yes	
If the woman had a		
companion with her, was		
the companion allowed to		
be with the pregnant		
woman during ANC	0 - No, 1 - Yes, -88 - Not	
consultation?	applicable (no companion)	
RMC subcomponent 3		0.25
The HCP asked how the		
pregnant woman was and		
asked about any problems	0 - No, 1 - Yes,	
RMC subcomponent 4		0.25
The HCP explained to the		
woman what they would		
like to do, prior to all		
examination or		
investigation	0 - No, 1 - Yes,	
The HCP explained that the		
findings of any		
examination and/or		
investigation would be	0 - No, 1 - Yes, -88 - Not	
confidential	applicable (no testing)	
The HCP explained the		
findings of investigations		
or examinations to the		
woman	0 - No, 1 – Yes	

EC2 = Screening for,			1
prevention and			
management of Anaemia			
Anaemia subcomponent 1			0.5
Blood taken to test	0 - No, 1 - Yes		
haemoglobin level	•		
If yes, HCP recognised and	0 - No, 1 – Yes, -88 Not		
acted upon abnormal	applicable		
findings			
Anaemia subcomponent 2			0.25
Iron tablets and folic acid	0 - No, 1 - Yes		
were given or prescribed			
for the pregnant woman			
Anaemia subcomponent 3			0.25
HCP counselled the	0 - No, 1 - Yes		
woman about dietary			
sources of iron			
Anaemia: Not in scoring			
If the woman was referred,			
what was the reason?	comment		
EC3 = Screening for Pre-			1
eclampsia			
Preeclampsia			0.5
Subcomponent 1			
The pregnant woman had			
her BP measured and			
noted in booklet	0 - No, 1 - Yes	0.1.	
If BP over 140/90 mmHg,		Only to	
HCP recognised and acted		appear if	
upon abnormal findings		answer to	
	0 - No, 1 – Yes, -88 – Not	previous question = 1-	
	applicable (BP normal)	Yes	
Preeclampsia	applicable (Br Hormal)	163	0.5
Subcomponent 2			0.5
The HCP checked urine for			
protein and noted in			
booklet	0 - No, 1 - Yes		
If yes, HCP recognised and	, , , , , , , , , , , , , , , , , , ,	Only to	
acted upon abnormal		appear if	
findings		answer to	
		previous	
		question = 1-	
	0 - No, 1 - Yes	Yes	
Preeclampsia: Not in			
scoring			
If the woman was referred,			
what was the reason?	comment		

EC4 = Screening for,			1
prevention and			
management of Malaria			
Malaria Subcomponent 1			0.5
HCP gave her the SP		Only to	
		appear if after	
	0 - No, 1 - Yes	1 st trimester	
HCP explained why it was		Only to	
important taking the SP		appear if	
		answer to	
		previous	
		question = 1-	
	0 - No, 1 - Yes	Yes	
HCP asked the woman			
whether she has			

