Insecticide treated bed net	0 - No, 1 - Yes		
If no, HCP provided		Only to	
Insecticide treated bed net		appear if	
		answer to	
		previous	
	O No 1 Voc	question = 1-	
Malaria Cubsampanant 2	0 - No, 1 - Yes	Yes	0.5
Malaria Subcomponent 2			0.5
Temperature taken using			
a thermometer and			
recorded in a booklet	0 - No, 1 - Yes		
Malaria testing was	O No 4 Van		
performed	0 - No, 1 – Yes	Onlinks	
If test done, did the		Only to	
woman test positive to malaria?	O No 1 Vos	appear if test performed	
If test was positive,	0 - No, 1 - Yes	•	
·	O No 1 Vos 99 Not	Only to	
antimalarials given to the woman	0 - No, 1 - Yes, -88 - Not applicable (Test negative)	appear if test performed	
If test was negative and	applicable (Test Hegative)	Only to	
woman had fever,		appear if test	
treatment or	0 - No, 1 – Yes, -88 – Not	performed	
complementary exams	applicable (Test positive,	periorined	
prescribed/given and	or test negative and		
noted in booklet	woman had no fever)		
If the woman was referred,	2		
what was the reason?	Comment		
EC5 = Screening for,			1
prevention and			
management of HIV			
If follow-up visit and			
previously tested for HIV,			
HIV antibody status was			
checked and noted in			
booklet	0 - No, 1 – Yes		

If ANC1 or no status	O No 1 Voc 99 Not	Ì	1
If ANC1 or no status	0 - No, 1 – Yes, -88 – Not		
indicated in booklet, HIV	applicable (Status		
testing was performed	indicated in booklet		
HCD as a self-state	already)	0.1.1.	
HCP counselled the		Only to	
woman prior to HIV test		appear if test	
	0 - No, 1 – Yes	performed	
HIV test result was noted		Only to	
in booklet		appear if test	
	0 - No, 1 – Yes	performed	
Did the woman test		Only to	
positive to HIV?		appear if test	
	0 - No, 1 – Yes	performed	
If test positive, first line		Only to	
ARV treatment was		appear if test	
prescribed or given and	0 - No, 1 – Yes, -88 – Not	performed	
noted in booklet	applicable (Test negative)		
If test positive, HCP		Only to	
counselled woman about		appear if test	
PMTCT	O No 1 Ves 99 Net	performed	
	0 - No, 1 - Yes, -88 – Not		
16.11	applicable (Test negative)		
If the woman was referred,			
what was the reason?	comment		
EC6 = Screening for,			1
prevention and			
management of Syphilis			
If follow-up visit, syphilis			
status was checked	0 - No, 1 - Yes		
If ANC1 or no status	0 - No, 1 - Yes, -88 – Not		
If ANC1 or no status indicated in booklet,	0 - No, 1 - Yes, -88 — Not applicable (Status		

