well being (or listened if			
she raised it)	0 - No, 1 – Yes		
If the woman expressed		Only to	
concern about her		appear if HCP	
psychological well-being,		asked or	
ie depression or anxiety,		woman raised	
the HCP counsels the		it	
woman	0 - No, 1 – Yes		
If the woman expressed		Only to	
concern about her		appear if HCP	
psychological well-being,		asked or	
ie depression or anxiety	0 - No, 1 - Yes, -88 - Not	woman raised	
the HCP refers the woman	Applicable (No concerns	it	
for additional support	expressed)	10	
Mental subcomponent 2	Слргеззеці		0.5
HCP asked the woman if			0.5
she is experiencing	0 No 1 Yes		
domestic abuse	0 - No, 1 – Yes	0.1.	
If the woman expressed		Only to	
concern about domestic		appear if HCP	
abuse, the HCP counsels	0 - No, 1 - Yes, -88 - Not	asked or	
the woman	Applicable (No concerns	woman raised	
	expressed)	it	
If the woman expressed		Only to	
concern about domestic		appear if HCP	
abuse the HCP refers the	0 - No, 1 - Yes, -88 - Not	asked or	
woman for additional	Applicable (No concerns	woman raised	
support	expressed)	it	
EC10 = Estimation of BMI			1
If subsequent visit, HCP		Only to	
checked if BMI previously		appear if	
recorded		subsequent	
	0 - No, 1 - Yes	visit	
BMI measured by HCP and	,	If ANC1: This	
noted		is the first	
		question to	
	If ANC1, answers are only	appear	
	= 0 - No, 1 – Yes	аррсаі	
	- 0 - NO, 1 - 165	If subsequent	
	If subsequent visit answers	visit, this is	
	•	the second	
	are = 0 - No, 1 - Yes		
	, -88 - Not applicable (BMI	question to	
If DMI do 40, LICD	already noted)	appear	
If BMI under 18, HCP	0 No 4 Var 00 No		
recognised and acted upon	0 - No, 1 - Yes-88 - Not		
abnormal findings (e.g.	applicable (BMI normal or		
provided nutrition advice	unchecked)	l	I

I	I	I	I .
and supplementation, or			
referred if signs of gravity)			
If BMI over 30, HCP	0 - No, 1 - Yes-88 - Not		
provided nutrition advice	applicable (BMI normal or		
	unchecked)		
EC11 = Prevention of post-			1
and pre-term birth			
HCP noted the gestational			
age in booklet	0 - No, 1 - Yes		
EC12 = Assessment of			
foetal wellbeing during			
pregnancy; Screening for			
multiple pregnancy,			
abnormal lie and			
presentation The HCD measured		Onlyannas	
The HCP measured		Only appears	
symphysis- fundal height		if age of pregnancy >	
	O No 1 Ves		
If fundal haight magazired	0 - No, 1 - Yes 0 - No, 1 - Yes, -88 - Not	16 weeks	
If fundal height measured,			
HCP recognised and acted	applicable (no abnormal		

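### In the Appendix 2 observation form, the urine follow-up and bed-net rows cannot be scored by the plan's own applicability rule, and the malaria-test row conflicts with Section 3.4

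*Protocol*

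**What the plan says.** Component numbers here follow Appendix 2, which swaps EC2 and EC3 relative to Section 3.4.

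- **Scoring rule.** The preamble of Appendix 2 gives each essential component one point (13 for ANC, 16 for PNC) and states that "Each subcomponent needs all applicable questions to be observed". Section 3.4 has the same intent: "some components are only applicable to a subset of clients, eg HCP counsels the woman about mental health is only applicable if" the client's earlier answer gives cause for concern.
- **Display rule.** The preamble says that boxes beginning with the word If appear only when their condition is met. It offers a not-applicable answer for items that depend on gestational age or visit type. Several rows also carry -88 for a clinical result, for example normal blood pressure.
- **Urine (EC3, subcomponent 2, weight 0.5).** The row beginning "The HCP checked urine for" is followed by a row on recognising and acting on abnormal findings. That row opens whenever urine was checked and offers 0 or 1.
- **Bed net (EC4, subcomponent 1, weight 0.5).** The form asks whether the provider enquired about a net. The next row, "If no, HCP provided" a net, opens when that answer is Yes and offers 0 or 1. The PNC row (EC4b) also offers only 0 or 1 and prints no trigger.
- **Malaria test (EC4 and EC4b, subcomponent 2, weight 0.5).** The row beginning "Malaria testing was" offers 0 or 1 for every woman. Section 3.4 defines the item as "Checked for clinical symptoms and test for Malaria if relevant". Appendix 1 lists the test without a condition.

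**The concern.** A rule that counts only applicable questions works only if the form records what makes a question applicable. For the urine and net rows it does not. If a provider checks urine, finds it normal and has nothing to act on, the observer must still choose No or Yes. If a woman already owns a net, the observer must still say whether one was provided.

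If such rows are entered as No and scored as printed, correct screening with nothing to act on scores the same as no screening: zero for that subcomponent. A provider who starts to check urine or ask about nets because of the training then gains no credit in those visits. If some observers enter Yes and others No, the score depends on an unwritten convention; Section 3.9.1 plans two data collectors. Once a visit is over, the deciding fact is lost, so no analysis plan can restore it.

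**Working it through.** **1. The weights.** ANC, from the scoring column of Appendix 2:
- single-score components EC5, EC6, EC8, EC10, EC11, EC12: 6 × 1 = 6 (EC12 has no printed weight; 1 is taken from the preamble);
- components with subcomponents: EC1 4 × 0.25; EC2 0.5 + 0.25 + 0.25; EC3, EC4, EC9 and EC13 2 × 0.5 each; EC7 0.2 + 0.4 + 0.4; together 7.

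The total is 13, with six binary and seven partial components, as Section 3.4 states.

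**2. Can applicability be derived from recorded fields?**

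| Row | Deciding fact | Recorded? |
|---|---|---|
| EC3 urine follow-up | urine normal or not | No. The blood pressure and haemoglobin rows have -88; this row does not |
| EC4, EC4b net provision | woman already has a net | No. Only whether the provider asked |
| EC4, EC4b malaria test | whether testing was relevant | Not for an untested woman. The form records that temperature was taken, not its value, and fever enters only after a test |
| EC9 psychological counselling | concern expressed | Yes. The next row has -88 for no concerns |
| EC6b syphilis treatment | test positive | Yes. The result is the preceding row |

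For the urine row, a scorer could count every 0 as not delivered, which penalises visits with normal urine. Or a scorer could count every 0 as inapplicable, which credits visits where an abnormal result was ignored. The recorded data cannot separate the two. The net row has the same problem.

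**3. Most that correct care can lose**, if each inapplicable row is entered as 0 and scored as not delivered:
- ANC, urine + net: (0.5 + 0.5)/13 = 7.7 points; maximum score 92.3%.
- ANC, adding the malaria test: 1.5/13 = 11.5 points; maximum 88.5%.
- PNC, net: 0.5/16 = 3.1 points.
- PNC, adding the malaria test: 1.0/16 = 6.3 points.

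**4. Effect on the estimated difference.** Let L be the affected weight and q the share of visits in which the conditions do not apply. The protocol gives no q, so a range is shown. Assume q is the same for each row, the training effect is equal across items, and inapplicable rows are entered as 0. Then observed effect = true effect × (1 − L·q/13). The true effect of 0.10 is the one used in the Section 3.6 simulations.

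| q | L = 1.0: ratio, reading of 0.10 | L = 1.5: ratio, reading of 0.10 |
|---|---|---|
| 0.25 | 0.981, 0.098 | 0.971, 0.097 |
| 0.50 | 0.962, 0.096 | 0.942, 0.094 |
| 0.75 | 0.942, 0.094 | 0.913, 0.091 |
| 1.00 | 0.923, 0.092 | 0.885, 0.088 |

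If the standard error is unchanged and the test is two-sided at 5% (assumed; no level is stated), power = Φ(2.80 × ratio − 1.96). A nominal 80% becomes about 78% to 70% with L = 1.5, and 79% to 73% with L = 1.0.

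**The case against.** **The rule counts only applicable questions, and scoring is done by the statistician.** This stands in part. Nothing in the protocol says that a 0 on an inapplicable row is a failure, and Section 3.4 mentions scoring algorithms. The scoring example at the end of Appendix 2 concerns respectful care, and its content is not shown. So a reader might infer that correct care is always scored as failure, but the text supports only that it can be. For normal urine an observer might equally enter Yes, so the direction of miscoding is not fixed. However, no algorithm can use a fact that was never collected.

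**The display rule for If boxes solves it.** It does not. The urine row is labelled by whether urine was checked, so it obeys the display rule and still appears for normal urine. The net row's label and printed trigger contradict each other, and the rule needs an ownership answer that the form lacks. The malaria row is not an If box.

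**EC9 counselling is the clearest fault, since Section 3.4 names that very item.** A reader might add it and reach 2.0/13 = 15.4 points. That is not supported as an irreparable loss, because the referral row below it records that no concern was expressed. EC6b is likewise derivable.

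**Malaria testing may be meant for every woman.** Appendix 1 is unconditional, and Section 2.1.3 regards low testing as missed opportunities. This stands: the row is a conflict between sections, and its 0.5 belongs in the total only if the conditional reading is adopted.

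**The tool is still to be finalised and pre-tested (Sections 3.7 and 3.9.1).** True, and this makes the correction cheap. It does not make the printed rows right.

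**Conclusion.** The urine follow-up and bed-net rows are wrong as printed: the form does not collect what its own scoring rule needs. At most this removes 7.7 points from the ANC maximum and 3.1 from the PNC maximum. If malaria testing is also conditional, the figures are 11.5 and 6.3. These are upper bounds, with every condition absent and every such row entered as 0.

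The consequence is attenuation and possible inconsistency between observers, not loss of the effect. With the three ANC rows, a true 0.10 would read about 0.097 to 0.088 under the assumptions in step 4.

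Two stronger readings should be avoided. The lost points should not be set against the 23-point detectable difference in Section 3.6: one is a ceiling on the level of the score, present before and after training, and the other is a difference between the two states. Nor does the sentence "The score will measure the proportion of essential components delivered in full" leave the scoring undefined. The same section goes on to allow intermediate scores, and Appendix 2 prints the weights, so the phrase is loose but the rule is determinate.

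**What to change.** Before the electronic form is deployed:

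1. Add -88 for normal urine to the EC3 follow-up row.
2. Add a field recording whether the woman already has a net, and trigger the provision row from that field in both EC4 and EC4b.
3. Reconcile the malaria-test row with the EC4 and EC4b definitions in Section 3.4 and with Appendix 1. Which clinical rule applies is for the investigators to decide. If it is conditional, record the condition for every woman, tested or not, and give the row a matching not-applicable code.
4. For consistency, add -88 for no concerns expressed to the EC9 psychological counselling row and -88 for a negative test to the EC6b treatment row. Both can otherwise be derived from neighbouring rows.

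The cost is a few edits to a form not yet in use, with a line on each in the data collectors' training. No extra visits or observers are needed. After observation begins, the missing urine and net facts cannot be recovered.
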